5.10.2 Subgroup analysis

For exploratory purposes subgroup analysis for the primary and secondary endpoints will be conducted, to assess whether the treatment effect differs according subgroups. The table below gives an overview of the subgroups that will be investigated and how they will be created:

Characteristic	Sub group
Age (years)	≤ median, > median
Sex	Male, Female
LVEF	≤ 40%, > 40%
Baseline NTproBNP (ng/L)	≤ median, > median

Characteristic	Sub group
Baseline eGFR (mL/min/1,73m ²)	≤ median, > median
Etiology of HF	Ischemic, non-ischemic
Home dose loop diuretic (mg)	≤ median, > median
Baseline Congestion score	≤ median, > median
Hyponatremia (mmol/L)	≤ 130, > 130
Thiazide	Yes, No
Atrial Fibrillation	Yes, No

The statistical model formulated for the analysis of the primary endpoints will be extended to include a fixed effect for the subgroup and an interaction term between the study arm and the subgroup. The interaction term allows for a subgroup-specific treatment effect. The interaction term will be considered significant at the 5% level.

Within each subgroup, summary statistics of the primary outcome by treatment arm will be presented; the OR for the treatment effect and 95% confidence interval. A p-value for the interaction test will also be reported. A forest plot, of the ORs (and 95%CI) per subgroup, will be used to summarize the results visually.

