4.3.4 Randomisation and blinding

The ADVOR study is a randomized double blind clinical trial with 2 treatment arms; therapy with high-dose loop diuretics and placebo vs therapy with high-dose loop diuretics and acetazolamide. An automated web-based system is used to randomly assign patients in a 1:1 ratio with variable blocks sizes, stratified for LVEF according to study centre. To ensure an equal proportion of HFpEF

versus HFREF patients in both study arms, the population will be stratified at inclusion according to LVEF $\leq 40\%$ versus $>40\%$. Permuted block randomization according to centre and LVEF stratum will be used to achieve this.

Patient, site personnel, sponsor personnel and data analysts will remain blinded to the identity of the treatment from the time of randomization until database lock. Though we do not foresee serious adverse events related to the study drug, the study code should only be broken for valid medical or safety reasons e.g. in the case of a severe adverse event where it is necessary for the investigator or treating health care professional to know which treatment the patient is receiving before the participant can be treated.

Following rules apply for unblinding;

- Rapid unblinding of a patient can be performed by a physician of the study team. Detailed information concerning the unblinding procedures is provided in the Manual of Operations.
- On receipt of the treatment allocation details, the PI or treating health care professional will continue to deal with the participant's medical emergency as appropriate.
- The PI/Investigation team documents the breaking of the code and the reasons for doing so on the medical notes and eCRF. It will also be documented at the end of the trial in any final study report and/or statistical report.

Unblinded data are to be kept strictly confidential until the time of unblinding of the trial and will not be accessible by anyone else involved in the trial with the following exceptions: (1) the Project Manager of the company responsible for the labelling and packaging of the IMP, (2) the IRT system programmers who work on the randomization and drug management system; and (3) the data manager who prepares reports required for regulatory reporting (suspected unexpected serious adverse reactions [SUSAR] reporting). These individuals will not be involved in the day-to-day running of the study.

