4.5 Sample Size

The ADVOR study is powered for primary endpoint which is the most relevant endpoint with respect to the study hypothesis and reliable data from large randomized clinical trials are available to make a formal power calculation.

In the DOSE trial, which recruited a similar study population as targeted in the ADVOR study, successful decongestion with a similar definition was approximately 11% vs 18% after 72 h in the low vs high-dose loop diuretics arm. The high-dose loop diuretics arm of the DOSE trial is quite comparable to the standard of care group in the ADVOR study as the loop diuretic dose used in the latter is only slightly lower (2x instead of 2.5x the oral maintenance outpatient dose) and non-loop diuretics, which were infrequently used in the DOSE trial, are not allowed. Because of these slight differences, 15% is chosen as an estimate for occurrence of the primary endpoint in the monotherapy with high-dose loop diuretics (SOC) group.

No reliable data are available from large clinical trials to estimate occurrence of the primary endpoint in the acetazolamide arm of the ADVOR study. Therefore, after thorough discussion with the advisory board a success rate of 25% was chosen, which represents a clear meaningful benefit of 10% more patients with appropriate decongestion after 72 h. Using both estimates, considering a type I error rate $\alpha=0.05$ and type II error rate $\beta=0.20$ (yielding a statistical power of 80%), the targeted sample size for the ADVOR study is calculated at $n = 494$. A 5% drop out has been calculated in order to estimate the total number of 519 patients to be enrolled in the study.

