5 STATISTICAL ANALYSIS

5.1 General principles

This statistical analysis plan dated 17 January 2022 is based on the statistical information documented in the study protocol version 2.0 dated 03 January 2019 (see section 10), the methods paper published in the European Journal of Heart Failure (2018)³ and guidance by the European Medicines Agency (EMA)⁴ and the Food and Drug Administration⁵ regarding the management of clinical trials during COVID-19 pandemic (2021).

The scope of this statistical analysis plan is to outline the statistical tools used for the primary and secondary objectives of the ADVOR study following the procedures documented in the study protocol version 2.0 dated 03 January 2019 in all participating centres.

Prior to the statistical analysis the collected study data will be cleaned by the data management team of the Clinical Trial Unit at the Ziekenhuis Oost-Limburg (ZOL-CTU). The cleaning will be performed according to the Data Management Plan agreed for the ADVOR trial.

All statistical hypothesis are 2-sided and a 5% significance level will be used. A correction for multiple testing will not be implemented.

Trial results will be reported according to the CONSORT statement on reporting randomized controlled trials.

For the analysis of the primary outcome, each secondary and exploratory outcome the following information will be presented:

- the number of patients included in each analysis, by treatment arm
- a summary statistic of the outcome (e.g. number (%), mean (SD)), by treatment arm

- the estimated treatment effect
- a 95% confidence interval for the estimated treatment effect
- A two-sided p-value for all analyses, a significance level of 5% will be used.

All statistical analysis will be done with Statistical Analysis System (SAS) for Windows, SAS 9.4.

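### Five numeric effect modifiers are tested for interaction only after a split at the sample median; a test on the uncut values should be added and would detect a gradient more often without new data

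*Combined protocol and SAP*

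**What the plan says.** SAP v2.0 section 5.10.2 lists eleven subgroup variables, as v1.0 does. Five are formed as "≤ median, > median": age, baseline NT-proBNP, baseline eGFR, home loop-diuretic dose and baseline congestion score. The rest are categories by nature (sex, aetiology, thiazide use, atrial fibrillation) or are cut at a value fixed beforehand (LVEF at 40%, sodium at 130 mmol/L).

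For the test, "The statistical model formulated for the analysis of the primary endpoints will be extended to include a fixed effect for the subgroup", plus an arm-by-subgroup term judged at 5%. Each subgroup gets an odds ratio with its confidence interval, shown in a forest plot, and the interaction p-value is reported.

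No treatment interaction with these five variables on their own scale is planned elsewhere. Protocol section 10.3 extends the models with explanatory variables but mentions no treatment interaction. The interaction in SAP section 5.10.4 concerns the COVID-19 period only. SAP Appendix A types age, eGFR, natriuretic peptide and furosemide dose as continuous and the congestion score as ordinal, so the uncut values are in the database. Sections 5.3 and 5.10.2 declare the subgroup analyses exploratory, without multiplicity correction.

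**The concern.** The trial is sized for the main effect, so its interaction tests start with little power. A median split treats a patient just above the median like one at the extreme and discards the gradient within each half. A real gradient with kidney function or degree of congestion is then more likely to be missed.

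Two features of this trial add to the problem. The congestion score is a sum of a few integers (protocol Figure 3), and home dose may take few distinct values. Patients tied at the median all fall in the lower group, so the two groups may be unequal. Section 5.10.2 also gives home dose in mg without naming one loop-diuretic equivalent, although the inclusion criteria contain a conversion.

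**Working it through.** **Inputs from the documents.** Testing: "All statistical hypothesis are 2-sided and a 5% significance level will be used" (SAP 5.1). Control rate: "15% is chosen as an estimate for occurrence of the primary endpoint"; active arm: "a success rate of 25% was chosen" (both SAP 4.5). Power 80% and 519 patients (4.5); allocation 1:1 (4.3.4). **Not in the documents, so assumed:** the distribution of each modifier, and the size and shape of any interaction.

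**1. The plan's own figure.** With unpooled variance, n per arm = (1.960 + 0.842)² × (0.15×0.85 + 0.25×0.75) / 0.10² = 7.849 × 0.315 / 0.01 = 247.2. Two arms of 247 give the stated 494. The pooled-variance formula gives 250 per arm, 500 in all (1.2% more). 494 × 1.05 = 518.7, the stated 519. The documents give no power figure for the interaction tests.

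**2. Information kept by a median split.** For an interaction linear in x, the efficiency of the split relative to the uncut test is the squared correlation between x and the indicator of x above its median. For a normal x the correlation is 0.3989 / 0.5 = 0.798, and its square is 2/π = 0.637. The loss is 36%. Then 519 × 0.637 = 330, so 519 patients act like about 330. Equal power would need 1/0.637 = 1.57 times as many patients.

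**3. The same quantity under other assumed distributions.**

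| Assumed modifier | Information lost |
|---|---|
| Discrete home dose (illustrative) | 22% |
| Uniform | 25% |
| Integer congestion score (three illustrative cases) | 32–33% |
| Normal | 36% |
| Exponential | 52% |
| Lognormal, log-SD 0.5 to 1.2, effect linear on the raw scale | 48–82% |

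For a lognormal marker whose effect is linear on the log scale, the loss is again 36%. In the illustrative congestion scores, 32% to 46% of patients lie above the median; in the illustrative home dose, 35% do.

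**4. Power.** Logistic model, 519 patients 1:1, 15% against 25% at the mean of x. The OR at the mean is (0.25/0.75)/(0.15/0.85) = 1.89, log-OR 0.636. x is standard normal with no effect in the control arm. Wald test of the interaction at 5%, 1,500 trials per setting, random centre effect omitted. The largest simulation standard error is √(0.25/1500) = 1.3 percentage points. The OR at ±1 SD is exp(0.636 ± b), where b is the interaction log-OR per SD.

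| b | OR at −1 SD | OR at +1 SD | Uncut | Median split |
|---|---|---|---|---|
| 0 (null) | 1.89 | 1.89 | 5.9% | 5.1% |
| 0.30 | 1.40 | 2.55 | 27% | 18% |
| 0.50 | 1.15 | 3.11 | 60% | 40% |
| 0.65 | 0.99 | 3.62 | 79% | 59% |
| 0.70 | 0.94 | 3.80 | 85% | 65% |

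**5. Other shapes**, scaled to unit variance, coefficient 0.5.

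| True shape | Uncut, linear | Median split |
|---|---|---|
| Step at the median | 44% | 55% |
| Step at +1 SD | 42% | 19% |
| U-shape | 8% | 6% |

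**The case against.** - **The tests are exploratory.** This stands. No decision rule, sample size or primary result depends on them, so the point is a modest improvement. The SAP does, however, report an interaction p-value against a 5% criterion, and it may as well come from the better test.
- **A median rule is set in advance and prevents picking a favourable cut.** This stands. A test on the uncut variable gives the same protection, provided its scale is fixed in advance.
- **Forest plots need groups.** They do, and the groups should stay. If the uncut p-value simply replaced the grouped one, plot and p-value would address different contrasts and could disagree. The uncut test should therefore be added and labelled.
- **The larger gains need large interactions.** Correct. At 0.7 per SD the OR falls slightly below 1 at −1 SD. At 0.3 per SD both tests are weak, 27% against 18%.
- **The uncut test assumes a shape.** Correct. It loses to the split if the effect changes exactly at the median. Nothing in the documents suggests a change there, and a step at +1 SD favours the uncut test.
- **The natriuretic peptide is not on one scale.** Correct. The inclusion criteria accept NT-proBNP or BNP, and note 8 to the protocol's procedures table makes NT-proBNP mandatory only for patients on sacubitril/valsartan. A rule is needed. The congestion score is ordinal, so a linear trend in it is a further assumption.

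**Conclusion.** The point holds as a cheap improvement to exploratory analyses; it is not an error in the plan. For a roughly normal modifier with an interaction linear in the log-odds, the split loses about 36% of the information and 9 to 20 percentage points of power over the range simulated. Both conditions are assumptions. Under other distributions the loss runs from about 22% to over 50%.

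A reader might infer more than the documents support:

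- **That the uncut test is free.** It needs no extra patients or data, but it assumes a functional form and is weaker for a step at the median.
- **That a third is always lost.** That figure belongs to one distribution and one shape.
- **That the sponsor will read a non-significant interaction as evidence of a uniform effect.** The SAP does not say so, and it reports subgroup odds ratios with confidence intervals.
- **That median groups cannot be reproduced elsewhere.** They can, once the cut value is reported; it is only unknown in advance.

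**What to change.** In SAP section 5.10.2, for the five variables now split at the median, add an interaction test of treatment by the uncut variable in the same mixed model, on these scales:

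- age and eGFR as measured;
- natriuretic peptide on the log scale, either from NT-proBNP values only or standardised within assay so that patients with BNP only can be included, with the choice stated;
- home dose on the log scale in one loop-diuretic equivalent, using the SAP's own conversion;
- congestion score as a linear trend.

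Fit a quadratic term, with its interaction with treatment, as a check on non-linearity and report it alongside. Name the uncut test as the main evidence on effect modification for these variables. Keep the median groups for the forest plot, with their odds ratios and the cut values stated, and label which p-value comes from which test. If treatment codes are already open when the change is made, present the uncut tests as a labelled addition.

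The cost is a short paragraph in the SAP, a functional-form assumption and a little more analysis. The tests remain exploratory.

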5.10.3 Treatment of missing data

The proposed statistical model assumes the missing data mechanism to be missing at random. If the level of missing data for the primary outcome in the ITTAS populations exceeds 5%, a sensitivity analysis to assess the robustness of the analysis of the primary outcome by means of multiple imputation technique will be performed for the primary endpoint.

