7.11 Withdrawal criteria

All subjects will be encouraged to remain on treatment and under observation for the full duration of the study. However, at any time during the study and without giving reasons, subjects may withdraw from the study at their own request or at the request of their legally acceptable representative. The subject will not suffer any disadvantage as a result.

It is important to note that discontinuation of study treatment (see section 8) is not the equivalent to withdrawal of informed consent. In cases where subjects indicate they do not want to "continue", investigators must determine whether this refers to discontinuation of study treatment (the most common expected scenario), unwillingness to attend the follow-up visit, unwillingness to have telephone contact, unwillingness to have any contact with study personnel, or unwillingness to allow contact with a third party (e.g., family member, doctor). Every effort must be made to continue to follow the subject until the end of the study.

In all cases, the reason for discontinuation (including "at the subject's request") must be recorded in the case report form (CRF) and in the subject's medical records.

No subject replacements are permitted in the study.

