10.3 Statistical analysis plan

- The treatment effect for the primary end-point [Treatment success (decongestion achieved) on the morning of day 4 without escalating diuretic strategy (doubling loop diuretic dose, addition of chlorthalidone, or ultrafiltration) during IV diuretic therapy on morning of day 3 is evaluated by means

of a generalized linear mixed model. The statistical model will include a fixed treatment effect and random center effect.

- For the first secondary end-point [occurrence of the combined endpoint of all-cause mortality and heart failure readmission during 3 months of follow-up], a generalized linear mixed model for a binary outcome will be used. The model will incorporate a fixed treatment effect and random center effect. If the treatment effect on the composite endpoint of 'all-cause mortality and HF readmission' turns out to be statistically significant, both components will be evaluated separately in a hierarchical fashion with HF readmissions first and all-cause mortality second. For this analysis, HF readmission will include patient dying from HF during the 3 months of FU. As a sensitivity analysis the worst case scenario, assuming a HF readmission for all patients dying to non HF related causes during the 3 month follow-up will be executed.
- Length of index hospitalization and change in quality of life scores are compared among treatment arms with a linear mixed model (fixed treatment effect and random center effect). Transformation will be employed when the model assumptions (such normality) are violated.
- All hypothesis are 2-sided and tested with a significance level of $\alpha=0.05$.

The proposed statistical models all assume the missing data mechanism to be missing at random. To investigate the sensitivity of the conclusions with respect to this assumption, a sensitivity analysis by means of multiple imputation technique will be performed.

Secondary Analysis:

- All statistical models discussed in the secondary analysis include a fixed treatment effect and random effect for the center, and in case of longitudinal outcome random patient effects (intercept, slope).
- The mixed models for the primary and secondary end-point analyses will be extended with explanatory variables (such as gender, age, race, ethnicity, kidney function, neurohumoral blockers, diuretics and blood pressure)
- For the end-points collected repeatedly over time, the rate of change will be investigated using longitudinal data models.

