4.3.1 STOP TREATMENT

The treating physician is allowed (but not obliged) to stop the study treatment, in case of persistent volume-overload in following cases:

- symptomatic hypotension with a systolic blood pressure <100 mmHg
- asymptomatic hypotension with a systolic blood pressure <90 mmHg
- an increase of serum Creatinine levels x 1.5 of the serum Creatinine level compared to admission value
- occurrence of metabolic acidosis (pH < 7.2)

The discontinuation of the study treatment will be seen as a failure for the primary endpoint (decongestion not achieved). However, if any of these events occur when the patient is judged to be euvolemic, the study treatment is stopped and the primary endpoint is considered to be successful (decongestion achieved).

Freedom from volume-overload (i.e. successful decongestion) on the morning of day 4 will be defined as not more than trace oedema, no residual pleural effusion, and no residual ascites (Figure 2).

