4.3.2 Treatment DOSE ADJUSTMENTS in case of an inappropriate diuretic response

If the total urinary output on the morning of day 3 is < 3500 mL and the patient is still volume overloaded, an escalation of decongestive treatment is mandatory. One of the outlined three options can be chosen at the discretion of the treating physician.

Escalation therapy options:

- doubling of the IV dose of the loop diuretics
- add oral chlorthalidone 50 mg once daily
- ultrafiltration or renal replacement therapy might be considered

The decision to proceed with escalation therapy will be collected in the case report as the need for escalation implies a failure for the primary endpoint.

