5.3 Multiplicity adjustment

There will be no correction for multiplicity of testing as there is only one primary endpoint. All other endpoints and subgroup analyses will be considered as exploratory.

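### The protocol promises an unconditional check of the missing-at-random assumption; SAP 5.10.3 runs it only above 5% missing, and the method named would not test that assumption

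*Combined protocol and SAP*

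**What the plan says.** Protocol v2.0, section 10.3, makes one assumption for every model: "The proposed statistical models all assume the missing data mechanism to be missing at random". It then commits to testing it: "To investigate the sensitivity of the conclusions with respect to this assumption, a sensitivity analysis by means of multiple imputation technique will be performed". No level of missingness is attached to that commitment.

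SAP v2.0, section 5.1, says the plan "is based on the statistical information documented in the study protocol version 2.0 dated 03 January 2019 (see section 10"), and it also names a 2018 methods paper and regulators' COVID-19 guidance as sources. Section 5.10.3 repeats the MAR assumption for the primary model but makes the follow-up conditional: "If the level of missing data for the primary outcome in the ITTAS populations exceeds 5%, a sensitivity analysis" by multiple imputation is performed, for the primary endpoint.

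Protocol v1.0 and v2.0 agree with each other on this, as do SAP v1.0 and v2.0, so the difference is not left over from an amendment. The SAP's document history records only the removal of two iron variables from the baseline table.

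Several rules reduce the number of missing primary outcomes. Under SAP 4.1.2, decongestion on the morning of day 2 or day 3 already counts as success. SAP 4.3.1 says: "The discontinuation of the study treatment will be seen as a failure for the primary endpoint (decongestion not achieved"). SAP 4.3.2 says that "the need for escalation implies a failure for the primary endpoint". Note 15 to the table in protocol 7.9 moves the day-4 assessments to discharge when discharge comes first.

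**The concern.** There are two separate difficulties.

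The first is the trigger. The protocol's check is unconditional, and the SAP withdraws it for any missingness up to 5% without saying why. Below the threshold no missing-data analysis remains. SAP 5.10.4 adds only a COVID-period term and efforts to record reasons for missing data, and no planned analysis uses those reasons.

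The second is the method. Imputation that draws missing outcomes from the distribution of the observed ones is itself valid only under MAR. It can use more information than the main model, but it cannot show what happens if missing patients differ from observed patients with the same recorded history. That is the question protocol 10.3 asks. Neither document gives an imputation model, a shift or a tipping point.

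What is at stake is whether a primary result close to 5% significance could be defended against the question of what the unobserved patients would have shown.

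**Working it through.** **1. The trigger.** 25/519 = 4.82%, so no check is run. 26/519 = 5.01%, so the check is run.

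**2. The plan's own figures.** SAP 4.5 gives 15% against 25%, two-sided alpha 0.05 and 80% power. The unpooled formula gives (1.960 + 0.842)² × (0.15 × 0.85 + 0.25 × 0.75) / 0.10² = 7.849 × 0.315 / 0.01 = 247.2 per arm. Taken as 247, this is 494 in total. Adding 5%: 494 × 1.05 = 518.7, or 519. Both figures reproduce, and nothing here changes them.

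**3. Imputation without a shift.** A simulation of 3,000 trials used true rates of 15% and 25%. Placebo outcomes were missing at random in 5%. Acetazolamide outcomes were missing only among failures, at 6.67% of them, which is about 5% of the arm. The true difference averaged 10.0 percentage points, the complete-case estimate 11.3, and imputation by arm 11.3. Imputation reproduced the bias and gave no sign of it.

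**4. How much missing outcomes could matter.** The documents give no expected number, so 5, 10 and 25 (the most that escapes the trigger) are shown. Assumptions: 260 acetazolamide and 259 placebo patients, the arm splits below, and no centre effect. The test is z = (p₁ − p₂) / √[p̄(1 − p̄)(1/n₁ + 1/n₂)], which is the uncorrected chi-square. Example: 62/247 against 37/247 gives p̄ = 99/494 = 0.2004, standard error 0.0360, z = 0.1012/0.0360 = 2.81, p = 0.005.

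The worst case counts every missing placebo patient as a success and every missing acetazolamide patient as a failure. The last column gives the missing patients counted as successes in each arm (P placebo, A acetazolamide) at which significance is lost.

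| Scenario, missing (A/P) | Observed A vs P | p observed | p all missing failed | p worst case | Significance lost at |
|---|---|---|---|---|---|
| Design, 3/2 | 64/257 vs 39/257 | 0.006 | 0.006 | 0.013 | never |
| Design, 5/5 | 64/255 vs 38/254 | 0.004 | 0.004 | 0.024 | never |
| Design, 13/12 | 62/247 vs 37/247 | 0.005 | 0.006 | 0.17 | P 7/12 with A 0/13 (p=0.053); P 10/12 with A 3/13 (p=0.058) |
| Borderline, 3/2 | 57/257 vs 39/257 | 0.042 | 0.044 | 0.076 | P 1/2 with A 0/3 (p=0.058); P 2/2 with A 1/3 (p=0.060) |
| Borderline, 5/5 | 57/255 vs 38/254 | 0.032 | 0.033 | 0.12 | P 2/5 with A 0/5 (p=0.058); P 3/5 with A 1/5 (p=0.060) |
| Borderline, 13/12 | 55/247 vs 37/247 | 0.037 | 0.041 | 0.52 | P 1/12 with A 0/13 (p=0.054); P 4/12 with A 3/13 (p=0.060) |

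**5. How extreme the design-effect reversals are.** If missing placebo patients succeeded at 15%, the chance of 7 or more of 12 is 0.067%, and of 10 or more about 3 in 10 million. The first reversal also needs all 13 missing acetazolamide patients to fail: 0.75¹³ = 2.4%. Jointly, 0.067% × 2.4% = 0.0016%. These chances assume that missing patients resemble observed ones, so they gauge how extreme the allocation is and are not evidence for MAR.

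**The case against.** The strongest reply is that this is a wording mismatch in a sensitivity analysis with little practical effect. Few outcomes should be missing, the design-effect result is robust, and a result with p between 0.03 and 0.05 is fragile to a handful of patients under any rule. Counting all missing patients as failures leaves every scenario in the table significant. Most of this stands, and it is why the severity is low. It is not a complete answer: at 54/247 against 37/247 (p = 0.048), counting all 25 missing as failures gives p = 0.052. Low missingness also makes the check cheap, which is no argument for dropping it.

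A second reply is that SAP 5.10.3 speaks only of robustness, not of testing MAR, and that the phrase used for the method does not exclude a delta-adjusted version. Both are true. But no such version is specified, and the protocol's stated purpose remains unmet.

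A third is that the methods paper or the regulators' guidance may explain the threshold. They are not available here, so the absence of a reason is established only for the protocol and SAP.

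A reader might infer two further faults. One is that restricting the check to the primary endpoint is wrong. SAP 5.3 answers that: "All other endpoints and subgroup analyses will be considered as exploratory". The restriction is defensible. The other is that withdrawals before day 4 need a new failure rule. Protocol 7.11 does separate the two events: "It is important to note that discontinuation of study treatment (see section 8) is not the equivalent to withdrawal of informed consent". However, a congested patient who withdraws while still on study treatment also stops it, and SAP 4.3.1 already scores that as failure. What is left is narrow and does not justify changing the primary endpoint definition so late.

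**Conclusion.** The concern holds in two respects. The SAP makes conditional a check that the protocol promised unconditionally, without a stated reason. And the check as described could not examine the assumption it was meant to examine.

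The severity is low. At the design effect, 5 or 10 missing outcomes cannot overturn significance, and 25 can do so only under extreme allocations. For an observed result near 22% against 15%, one to four missing placebo patients counted as successes are enough, depending on how the missing acetazolamide patients fared. These figures rest on unadjusted tests, assumed arm splits and an unknown number of missing outcomes.

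It is tempting to note that planned dropout is 519 − 494 = 25 patients, one short of the trigger, and to conclude that the check would be skipped at exactly the expected missingness. The documents do not support that. The 5% dropout allowance is for the trial as a whole and is not a forecast of missing day-4 outcomes, which the endpoint rules should keep lower. Nor do the documents support reading this as a threat to the primary conclusion in general.

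**What to change.** Amend SAP 5.10.3 before unblinding:

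- Delete the 5% trigger.
- For any primary outcome still missing under the existing rules, run multiple imputation separately by arm, using the available day 2 and day 3 volume scores and the urine output.
- Add a delta-adjusted (tipping-point) version by arm, reporting how far the missing outcomes must depart from MAR before the conclusion changes.
- Within the tipping-point range, include the scenario in which early withdrawals not already scored by SAP 4.3.1 count as failures. This covers the remaining ambiguity without touching the primary endpoint definition.

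The cost is SAP wording and a few extra SAS runs. The scores and urine volumes are already collected under protocol 7.7.2 and Appendix 4, so no new data are needed and the sample size does not change.
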